9 CLINICAL MONITORING

Clinical site monitoring is conducted to ensure:

- that the rights of the participants are protected;
- that the study is implemented per the approved protocol, Good Clinical Practice and standard operating procedures; and,
- the quality and integrity of study data and data collection methods are maintained.

Monitoring for this study will be performed by NCI CCR Office of Sponsor and Regulatory Oversight (OSRO) Sponsor and Regulatory Oversight Support (SROS) Services contractor. Clinical site monitoring activities will be based on OSRO standards, FDA Guidance E6(R2) Good Clinical Practice: Integrated Addendum to ICH E6(R1) March 2018, and applicable regulatory requirements.

Details of clinical site monitoring will be documented in a Clinical Monitoring Plan (CMP) developed by OSRO. CMPs will be protocol-specific, risk-based and tailored to address human subject protections and integrity of the study data. OSRO will determine the intensity and

frequency of monitoring based on several factors, including study type, phase, risk, complexity, expected enrollment rate, and any unique attributes of the study and the site. The Sponsor will conduct a periodic review of the CMP to confirm the plan's continued appropriateness. A change to the protocol, significant or pervasive non-compliance with GCP, or the protocol may trigger CMP updates.

OSRO SROS Monitoring visits and related activities will be conducted throughout the life cycle of each protocol. The first activity is before the study starts to conduct a Site Assessment Visit (SAV) (as warranted), followed by a Site Initiation Visit (SIV), Interim Monitoring Visit(s) (IMVs), and a study Close-Out Visit (COV).

Some monitoring activities may be performed remotely, while others will occur at the study site(s). Monitoring visit reports will describe visit activities, observations, and associated action items or follow-up required for resolution of any issues, discrepancies, or deviations. Monitoring reports will be distributed to the study PI, NCI CCR QA, CCR Protocol Support Office, coordinating center (if applicable), and the Sponsor regulatory file.

The site Monitor will inform the study team of any deviations observed during monitoring visits. If unresolved, the Monitor will request that the site Staff enter the deviations in the CCR Protocol Deviation Tracking System (PDTs) for deviation reporting to the Sponsor and as applicable per institutional and IRB guidance.

10 HUMAN PARTICIPANTS PROTECTION

10.1 Institutional Review Board

Each site principal investigator will obtain IRB approval for this protocol to be conducted at his/her research site(s) and send supporting documentation to the CCR before initiating recruitment of participants. The investigator will submit applicable information to the IRB on which it relies for the review, to conduct the review in accordance with 45 CFR 46, ICH E6 GCP, and as applicable, 21 CFR 56 (Institutional Review Boards) and 21 CFR 50 (Protection of Human Participants), other federal, state, and local regulations. The IRB must be registered with OHRP as applicable to the research. CCR must receive the documentation that verifies IRB-approval for this protocol, associated informed consent documents, and upon request any recruitment material and handouts or surveys intended for the participants, prior to the recruitment and enrollment of participants.

Any amendments to the protocol or consent materials will be approved by the IRB before they are implemented. IRB review and approval will occur at least annually throughout the enrollment and follow-up of participants and may cease if annual review is no longer required by applicable regulations and the IRB. The investigator will notify the IRB of deviations from the protocol and reportable SAEs, as applicable to the IRB policy.

Each institution engaged in this research will hold a current Federalwide Assurance (FWA) issued by the Office of Human Research Protection (OHRP) for federally funded research.

Of note for this study: A single IRB of record, *NIH IRB*, will be accountable for compliance with regulatory requirements for this multi-centered study, at participating sites. A reliance agreement will be required. The reliance agreement and local policy will set forth the specific responsibilities of the IRB and each participating site. Participating sites will then rely on the IRB of record to satisfy the regulatory requirements relevant to the IRB review. The participating sites will maintain essential required documentation of IRB reviews, approvals, and correspondence, and must provide copies of any agreements and essential documentation to the CCR or regulatory authorities upon request.

10.2 Informed Consent Process

Informed consent is a process that is initiated prior to an individual agreeing to participate in a trial and continuing throughout the individual's trial participation. Before any study procedures are performed, informed consent will be obtained in-person or remotely (e.g., via telephone or other NIH/local approved remote secure internet-based platforms used in compliance with policy including HRPP Policy 303) and documented. Participants will receive a concise and focused presentation of key information about the clinical trial, verbally and with a physical or electronic consent form. The explanation will be organized and presented in lay terminology and language that facilitates understanding why one might or might not want to participate.

An investigator or designee will describe the protocol to potential participants in-person or remotely. The key information about the purpose of the study, the procedures and experimental aspects of the study, risks and discomforts, any expected benefits to the Participant, and alternative treatment will be presented first to the Participant.

Participants will also receive an explanation that the trial involves research, and a detailed summary of the proposed study procedures and study interventions/products. This will include aspects of the trial that are experimental, the probability for random assignment to treatment groups, any expected benefits, all possible risks (including a statement that the particular treatment or procedure may involve risks to the Participant or to the embryo or fetus, if the Participant is or may become pregnant, that are currently unforeseeable), the expected duration of the Participant's participation in the trial, alternative procedures that may be available and the important potential benefits and risks of these available alternative procedures.

Participants will be informed that they will be notified in a timely manner if information becomes available that may be relevant to their willingness to continue participation in the trial. Participants will receive an explanation as to whether any compensation and any medical treatments are available if injury occurs, and, if so, what they consist of, or where further information may be obtained. Participants will be informed of the anticipated financial expenses, if any, to the Participant for participating in the trial, as well as any anticipated prorated payments, if any, to the Participant for participating in the trial. They will be informed of whom to contact (e.g., the investigator) for answers to any questions relating to the research project.

Information will also include the foreseeable circumstances and/or reasons under which the Participant's participation in the trial may be terminated. The participants will be informed that participation is voluntary and that they are free to withdraw from the study for any reason at any time without penalty or loss of benefits to which the Participant is otherwise entitled.

The extent of the confidentiality of the participants' records will be defined, and participants will be informed that applicable data protection legislation will be followed. Participants will be informed that the monitor(s), auditors(s), IRB, NIH, and regulatory authority(ies) will be granted direct access to the Participant's original medical records for verification of clinical trial procedures and/or data without violating the confidentiality of the Participant, to the extent permitted by the applicable laws and regulations, and that, by signing a written informed consent form, the Participant is authorizing such access.

Participants will be informed that records identifying the Participant will be kept confidential, and, to the extent permitted by the applicable laws and/or regulations, will not be made publicly available and, if the results of the trial are published, the Participant's identity will remain confidential. Participants will be informed whether private information collected from this research and/or specimens will be used for additional research, even if identifiers are removed.

Participants will be allowed sufficient time to consider participation in this research trial and have the opportunity to discuss this trial with their family, friends or legally authorized representative, or think about it prior to agreeing to participate.

Informed consent forms will be IRB-approved and participants will be asked to read and review the consent form. Participants must sign the informed consent form prior to starting any study procedures being done specifically for this trial.

Once signed, a copy of the informed consent form will be given to the Participant(s) for their records. The Participant(s) may withdraw consent at any time throughout the course of the trial. The rights and welfare of the Participant(s) will be protected by emphasizing to them that the quality of their medical care will not be adversely affected if they decline to participate in this study.

Consent will be documented with required signatures on the physical document (which includes the printout of an electronic document sent to participant) or on the electronic document.

Manual (non-electronic) signature on electronic document:

When a manual signature on an electronic document is used for the documentation of consent at the NIH Clinical Center, this study will use the following to obtain the required signatures:

- Adobe platform (which is not 21 CFR Part 11 compliant); or,
- iMedConsent platform (which is 21 CFR Part 11 compliant)

During the consent process, participants and investigators will view individual copies of the approved consent document on screens at their respective locations (if remote consent); the same screen may be used when in the same location but is not required.

Both the investigator and the participant will sign the document using a finger, stylus or mouse.

Note: Refer to the CCR SOP PM-2, Obtaining and Documenting the Informed Consent Process for additional information (e.g., verification of participant identity when obtaining consent remotely) found at:

<https://ccrod.cancer.gov/confluence/pages/viewpage.action?pageId=73203825>.

Please see site specific supplement for electronic signature requirements for participating site.

Study personnel may employ recruitment efforts prior to obtaining study consent if a patient-specific screening consent is on record or if the IRB has agreed that chart review is allowed without a fully executed screening consent. In cases where there is not a patient-specific screening consent on record, site Clinical staff may pre-screen via chart review and refer potential participants to the Research staff. Research staff would obtain written consent per the standard informed consent process before conducting protocol-specific screening activities.

New information will be communicated by the site principal investigator to participants who consent to participate in this trial in accordance with IRB requirements. The informed consent document will be updated and participants will be re-consented per IRB requirements, if necessary. Participants will be given a copy of all informed consent forms that they sign.

10.3 Consent for Future Use of Stored Specimens and Data

Residual samples/specimens are those that are left over after protocol-specified testing and this study has been completed. Participants will be asked for permission to keep any remaining (residual) specimens (serum and PBMCs) derived from venous blood samples for possible use in future research studies, such as examining additional immunological assessments or testing for antibodies against other viruses or bacteria. These residual specimens will be stored coded indefinitely at NIH or designated NIH site. Specimens may be shared per protocol or as allowed per informed consent with any additional review and approval by an IRB, if required.. The recipients of specimens will be informed that these specimens have a NIH certificate of confidentiality.

10.4 Exclusion of Women, Minorities, and Children (Special Populations)

Both men and women are eligible for this trial if they meet eligibility criteria. Participants from all racial and ethnic groups are eligible for this trial. All participants meeting the criteria listed in section 2.1 are eligible for enrollment.

There are no dosing or adverse event data are currently available on the use of 2019 nCov Vaccine in participants <18 years of age; therefore, children are excluded from this study.

10.5 Participant Confidentiality

Participant confidentiality is strictly held in trust by the participating investigators, their staff, and the sponsor(s) and their agents. This confidentiality includes documentation, investigation data, Participant's clinical information, and all other information generated during participation in the study. No information concerning the study or the data generated from the study will be released to any unauthorized third party without prior written approval of the CCR and the Participant. Participant confidentiality will be maintained when study results are published or discussed in conferences. The study monitor or other authorized representatives of the sponsor or governmental regulatory agencies may inspect all documents and records required to be maintained by the investigator, including but not limited to, medical records (office, clinic, or hospital) and pharmacy records for the participants in this study. The clinical study site will permit access to such records.

All records will be kept locked and all computer entry and networking programs will be carried out with coded numbers only and with password protected systems. All non-clinical specimens, evaluation forms, reports, and other records that leave the site will be identified only by a coded number.

10.6 Certificate of Confidentiality

To protect privacy, we have received a Certificate of Confidentiality. With this Certificate, the researchers cannot be forced to release information that may identify the research Participant, even by a court subpoena, in any federal, state, or local civil, criminal, administrative, legislative, or other proceedings. The researchers will use the Certificate to resist any demands for information that would identify the Participant, except as explained below.

The Certificate cannot be used to resist a demand for information from personnel of the United States Government that is used for auditing or evaluation of federally funded projects, like this study, or for information that must be released in order to meet the requirements of the Federal Food and Drug Administration (FDA).

A Certificate of Confidentiality does not prevent the Participant from voluntarily releasing information about themselves or their involvement in this research. If any person or agency obtains a written consent to receive research information, then the researchers may not use the Certificate to withhold that information.

The Certificate of Confidentiality does not prevent the researchers from reporting without the Participant's consent, information that would identify the Participant as a participant in the research project regarding matters that must be legally reported including: child and elder abuse, sexual abuse, or wanting to harm themselves or others.

The release of individual private information or specimens for other research will only occur if consent was obtained from the individual to whom the information, document, or biospecimen pertains, or for the purposes of other research that is in compliance with applicable Federal regulations governing the protection of human participants in research.

10.7 Costs, Participant Compensation, and Research Related Injuries

10.7.1 NIH

Costs:

There is no cost for the research tests, procedures, and study product that participants receive at the NIH Clinical Center while taking part in this trial. If some tests and procedures are performed outside the NIH Clinical Center, these may be billed to the Participant, Participant's insurance or third party. Medicines that are not part of the study treatment will not be provided or paid for by the NIH Clinical Center.

Participant Compensation:

Participants will not be compensated on this study.

The NCI will cover the costs of some expenses associated with protocol participation. Some of these costs may be paid directly by the NIH and some may be reimbursed to the

participant/guardian as appropriate. The amount and form of these payments are determined by the NCI Travel and Lodging Reimbursement Policy.

10.7.2 Participating Sites

This will be based on local guidelines (e.g., as described in the site-specific consent).

10.7.3 All Sites

If it is determined by the site principal investigator that an injury occurred to a Participant as a direct result of the tests or treatments that are done for this trial, then referrals to appropriate health care facilities will be provided to the Participant. Study personnel will try to reduce, control, and treat any complications from this trial. Immediate medical treatment may be provided by the participating site.

The Secretary HHS issued a Public Readiness and Emergency Preparedness (PREP) Act Declaration for certain COVID-19 countermeasures in March 2020. While study participants right to sue for significant injuries (including death) is restricted under the Declaration, U.S.-located or other certain participants with a U.S. nexus may be able to seek compensation from HRSA's Countermeasure Injury Compensation Program (CICP) for certain serious physical injuries. Participants will be notified of the same in the informed consent document.

11 STATISTICAL CONSIDERATIONS

11.1 Study Hypotheses

There is no hypothesis testing in this study; the study is intended to develop modestly precise estimates of parameters which reflect potential efficacy.

11.2 Sample Size Considerations

The number of proposed participants is considered sufficient to provide a descriptive summary of the immunogenicity and safety of mRNA-1273 with reasonable precision overall and in various cohorts of participants.

It will be assumed that there is a maximum of 220 participants available for evaluation, but that subsets of 20 and 30 participants may be considered as well, primarily based on the sub-cohorts for hematological malignancies. In addition, early results any cohort may be reported prior to final study completion after evaluation of day 57 lab results. Overall, there will be 20 evaluable participants with solid tumors and 60 participants with hematologic malignancies in the vaccine-naïve cohorts. The booster vaccine cohorts will have a maximum enrollment of 20 participants with the exception of the CAR T cell therapy cohort which will have a maximum enrollment of 30 participants and the Other Adult Solid Tumor cohort which has a maximum enrollment of 10 participants. Participants enrolled onto the vaccine naïve cohort who receive a booster dose will not be counted towards these totals.

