| SOP | Standard Operating Procedure |
| SUSAR | Suspected Unexpected Serious Adverse Reaction |
| US | United States |
| WHO | World Health Organization |

PROTOCOL SUMMARY

Title: A Trial of the Safety and Immunogenicity of the COVID-19 Vaccine (mRNA-1273) in Participants with Hematologic Malignancies and Various Regimens of Immunosuppression, and in Participants with Solid Tumors on PD1/PDL1 Inhibitor Therapy, Including Booster Doses of Vaccine

Design of the Study: This is an open-label, multicenter clinical trial designed to evaluate the safety, reactogenicity and primary immunogenicity of the mRNA-1273 vaccine administered in 2 doses, 28 days apart, in participants who have hematological malignancy and are immunosuppressed due to their disease and/or treatment or receiving a PD-1/PDL-1 inhibitor for treatment of a solid tumor can be associated with appropriately high rates of development of neutralizing antibodies of mRNA-1273. The trial will also evaluate the safety, reactogenicity and immunogenicity after administration of additional “booster” doses of the vaccine.

Study Phase: 2

Study Population: For the vaccine-naïve cohorts, up to 80 participants will be enrolled.

- 20 participants with solid tumor malignancies who have initiated PD1/PDL1 inhibitor therapy as part of standard of care and are deemed to have a stable regimen without the need for any immunosuppressive therapy or corticosteroids.
- 60 participants with leukemia, lymphoma, multiple myeloma and participants post-allogeneic stem cell transplant will be enrolled based on their perceived risk of immunosuppression.

For the previously-vaccinated (also known as “booster”) cohorts, up to 140 participants will be enrolled for booster injections. All participants on the vaccine-naïve cohorts will have the option of receiving boosters; however, they will not count towards the maximum accrual goal for each of the booster groups. Note: All participants will be eligible to receive up to three (3) booster doses of vaccine on study.

- 20 participants with solid tumor malignancies who have initiated PD1/PDL1 inhibitor therapy as part of standard of care and are deemed to have a stable regimen without the need for any immunosuppressive therapy or corticosteroids.
- 20 participants with chronic lymphocytic leukemia who are not currently on any therapies
- 20 participants with chronic lymphocytic leukemia who are on BTK inhibitor therapy alone

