3 STUDY DESIGN, OBJECTIVES AND ENDPOINTS OR OUTCOME MEASURES

3.1 Study Design Description

This is an open-label, multicenter clinical trial designed to evaluate the safety, reactogenicity and primary immunogenicity of the novel LNP-encapsulated mRNA-based vaccine that encodes for a full-length, prefusion stabilized spike (S) protein of SARS-CoV-2 manufactured by ModernaTX, Inc. in a specific population of patients with either hematologic malignancies under active treatment or patients with solid tumors who are undergoing treatment with PD1/PDL1 inhibitors.

For the vaccine-naïve cohorts, the vaccine will be administered in 2 doses, 28 days apart. Up to 80 participants will be enrolled into one of four vaccine-naïve cohorts. Participants will receive an IM injection (0.5 mL) of mRNA-1273 on Day 1 and Day 29 in the deltoid muscle and will be followed through 12 months post second vaccination (Day 394).

For the booster-vaccine cohorts, the booster vaccine will be administered in a single dose. Up to 120 participants will be enrolled into one of 6 booster-vaccine cohorts. Participants will receive an IM injection (0.5 mL) of mRNA-1273 on Day 1 in the deltoid muscle and will be followed through 12 months post vaccination (Day 360). For participants who choose to receive an additional (second) booster dose of the vaccine, the second booster dose of mRNA-1273 must be administered at least 4 weeks after their previous dose of the vaccine. Similarly, for participants who choose to receive a third booster dose of the vaccine, the third booster dose of mRNA-1273 must be administered at least 4 weeks after their previous dose of the vaccine. Note: Participants may enroll on this study only to receive a second or a third booster dose and will be counted/analyzed in the identified booster-vaccine cohorts.

Participants initially enrolled in the vaccine naïve cohort will also have the option to receive the first booster dose no less than 4 weeks after their second dose; with the similar option for a second or third booster on the same schedule as the booster-vaccine cohorts. If they choose to receive this, they will adhere to the booster vaccine calendar and will be analyzed also as part of the booster vaccine group.

Safety data will be reviewed by the assigned Safety Monitoring Committee (SMC) as explained in section [8.10.1](#).

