3.2 Study Objectives and Endpoints

| Objectives and Endpoints | |
|--|--|
| Primary Objective | Primary Endpoints |
| Safety Objective: To evaluate the safety and reactogenicity of the mRNA-1273 vaccine administered in 2 doses 28 days apart, in participants who have a | Safety Endpoints: 
Solicited local and systemic Adverse Reactions (ARs) through 7 days after each injection. |

| Objectives and Endpoints | |
|--|---|
| Primary Objective | Primary Endpoints |
| hematological malignancy and are immunosuppressed due to their disease and/or treatment, or receiving a PD-1/PDL-1 inhibitor for treatment of a solid tumor for participants who are vaccine- naïve. To evaluate the safety and reactogenicity of booster doses of mRNA-1273 vaccine administered to participants with cancer who have previously received an mRNA or alternative vaccine regimen | 
Unsolicited AEs through 28 days after each injection.SAEs throughout the entire study period.Vital sign measurements and physical examination findings. |
| Immunogenicity Objective: To assess the immunogenicity of mRNA-1273 in participants with cancer, as assessed by the titer or level of specific binding antibody (bAb) | Immunogenicity Endpoints: 
Titer or level of specific binding antibody (bAb), in participantsTiter or level of SARS-CoV-2-specific binding antibody (bAb) measured by ELISA on Day 1, Day 29, Day 36, Day 57 Day 209 and Day 394 for participants on Vaccine-Naïve CohortsTiter or level of SARS-CoV-2-specific binding antibody (bAb) measured by ELISA on Day 1, Day 29, Day 180, Day 360 for participants on Booster Vaccine Cohorts |

| Secondary Objective | Secondary Endpoints |
|---|--|
| To evaluate the immunogenicity of the mRNA-1273 vaccine administered, as assessed by the titer or level of neutralizing antibody (nAb). | For Vaccine-Naïve Cohorts: 
Titer or level of SARS-CoV-2-specific neutralizing antibody (nAb) on Day 1, Day 29, Day 36, Day 57, Day 209, and Day 394Seroconversion due to vaccination on Day 29, Day 36, Day 57, Day 209, and Day 394 measured as:
For subjects with no detectable antibody titer (< |

| Secondary Objective | Secondary Endpoints |
|---------------------|---|

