11.4.2.2 Safety Analyses

Safety and reactogenicity will be assessed by clinical review of all relevant parameters including solicited ARs (local and systemic events), unsolicited AEs, SAEs, AEs leading to discontinuation, safety laboratory test results, vital signs, and physical examination findings.

Solicited ARs and unsolicited AEs will be coded by system organ class (SOC) and preferred term according to the MedDRA for adverse reaction terminology. The Toxicity Grading Scale for Healthy Adult and Adolescent Volunteers Enrolled in Preventative Vaccine Clinical Trials (DHHS 2007) is used in this study with modification for rash, solicited ARs, unsolicited AEs, and vital signs.

Rash will be graded as:

- Grade 0 = no rash
- Grade 1 = localized without associated symptoms
- Grade 2 = maculopapular rash covering $< 50\%$ body surface area
- Grade 3 = urticarial rash covering $> 50\%$ body surface area
- Grade 4 = generalized exfoliative, ulcerative or bullous dermatitis

All safety analyses will be based on the Safety Set, except summaries of solicited ARs which will be based on the Solicited Safety Set. All safety analyses will be provided overall and by cohort.

The number and percentage of participants with any solicited local AR, with any solicited systemic AR and with any solicited AR during the 7-day follow-up period after each injection will be provided with a 2-sided 95% exact CI using the Clopper-Pearson method.

Number and percentage of participants with unsolicited AEs, SAEs, Grade 3 or higher ARs and AEs, treatment-related AEs and SAEs, and AEs leading to discontinuation from study vaccine or participation in the study will be summarized. Unsolicited AEs will be summarized by system organ class and/or preferred term coded by MedDRA.

For treatment-emergent safety laboratory tests results, the raw values and change from baseline values will be summarized by timepoint.

The number and percentage of participants who have chemistry, hematology, coagulation, and vital signs results below or above the laboratory normal ranges will be tabulated by timepoint.

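### Safety is summarised overall and by cohort but never by arm, so the overall figure mixes two-dose vaccine-naïve and booster participants and estimates neither primary safety objective

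*Combined protocol and SAP*

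**What the plan says.** **Numbers.** The Protocol Summary gives two accrual limits: "For the vaccine-naïve cohorts, up to 80 participants will be enrolled" and "up to 140 participants will be enrolled for booster injections". Section 11.2 adds them ("It will be assumed that there is a maximum of 220 participants available for evaluation") and calls the number sufficient to describe immunogenicity and safety "with reasonable precision overall and in various cohorts of participants". Section 3.1 gives a different booster figure: "Up to 120 participants will be enrolled into one of 6 booster-vaccine cohorts".

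**Objectives.** Section 3.2 and the Protocol Summary state separate primary safety objectives for the two-dose series in vaccine-naïve participants and for booster doses in previously vaccinated participants.

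**Safety analysis.** Section 11.4.1.4 defines the Safety Set as everyone with at least one study injection, in either arm. Section 11.4.2.2 sets the reporting levels: "All safety analyses will be provided overall and by cohort". It names no arm-level summary.

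**Subgroups.** Section 11.4.2.5 refers to four cohorts and to hematologic versus solid tumor, without naming an arm. Section 4.6 has eleven cohorts in two arms.

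**Participants in both groups.** Under section 3.1, naïve participants who take a booster "will be analyzed also as part of the booster vaccine group". Section 11.2 leaves them out of the booster totals.

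**The concern.** The trial tests no hypotheses (section 11.1), so its statistical output consists of estimates and intervals. Each needs a clear population and denominator.

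An overall adverse-event percentage across both arms combines people receiving their first COVID-19 vaccine doses, with two scheduled injections, and people already vaccinated, with one to three booster injections. The regimens, vaccination histories and collection windows differ, and the mix is set by how many people each arm happens to enrol. With no arm-level line beside it, the overall row is the only summary above single-cohort level, and it is the one a reader will quote.

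The subgroup section appears to predate the booster arm. The handling of boosted naïve participants is also left open, so the denominators of booster-group tables cannot be read from the plan.

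**Working it through.** **1. The plan's figure.** Cohort maxima from section 4.6: naïve 4 × 20 = 80; booster 20 + 20 + 30 + 20 + 20 + 20 + 10 = 140; total 220. This reproduces section 11.2. With section 3.1's booster figure the total is 80 + 120 = 200, which does not.

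**2. What the overall percentage estimates.** With true rates p₁ (naïve) and p₂ (booster), and each person counted once:

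overall = (80·p₁ + 140·p₂) / 220 = 0.364·p₁ + 0.636·p₂.

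For a difference d between the arms, the overall rate lies 0.636·d from the naïve rate and 0.364·d from the booster rate. The documents give no d; as assumptions:
- d = 10 points: 6.4 and 3.6 points away;
- d = 20 points: 12.7 and 7.3 points away.

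The weight also moves with accrual. If the naïve arm only half fills, it is 40/180 = 0.222; if the booster arm only half fills, it is 80/150 = 0.533. At d = 10 points the overall rate then differs by (0.533 − 0.222) × 10 = 3.1 points between the two cases, although neither arm's true rate has changed. These accrual shortfalls are also assumptions.

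**3. Collection windows.** Section 3.2 collects unsolicited AEs through 28 days after each injection.
- Naïve: injections on Days 1 and 29, so collection runs to Day 57, about 56 days.
- Booster: 28 days for one injection, up to 3 × 28 = 84 days for three.
- A naïve participant who takes boosters can have up to five study injections.

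A percentage of participants with any unsolicited AE depends on this exposure.

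**4. Precision at each N.** 95% Clopper-Pearson interval, with lower limit the 2.5% quantile of Beta(x, n − x + 1) and upper limit the 97.5% quantile of Beta(x + 1, n − x):

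| n | half-width at 50% | half-width at 10% | upper limit, 0 events |
|---|---|---|---|
| 220 | 6.8 points | 4.2 points | 1.7% |
| 140 | 8.6 points | 5.3 points | 2.6% |
| 80 | 11.4 points | 7.2 points | 4.5% |

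At d = 10 points, the 6.4-point distance between the overall and naïve rates is about as large as the 6.8-point half-width at n = 220.

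**5. Antibody days.** For the primary binding-antibody endpoint, section 3.2 lists Days 1, 29, 36, 57, 209 and 394 for naïve cohorts and "Day 1, Day 29, Day 180, Day 360 for participants on Booster Vaccine Cohorts". The only shared post-baseline label is Day 29. In naïve cohorts that sample is drawn before dose 2 (section 7.3.2.1), so it reflects one first-ever dose. In booster cohorts it is 28 days after a booster. Day 57 neutralizing antibody is also in both schedules, about 28 days after dose 2 in one and 56 days after a booster in the other. A shared label does not mean a shared exposure.

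**The case against.** The strongest reply is that little here is actually wrong. The 220 is a correct count of distinct people, and the safety summaries are counts of participants, which naturally take each person once. Solicited reactions are already tabulated after each injection. Cohort rows are planned, so a reader could add cohorts 1 to 4 and 5 to 11. The booster cohorts are themselves mixed in vaccination history.

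Much of this stands. But adding cohort rows yields no planned arm-level interval, and it fails if boosted naïve participants are included in the booster rows without being identified. Mixture within the booster arm is no reason to mix the arms, because the booster objective is written for that broad group.

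A reader might infer three stronger conclusions. The documents do not support them.
- *That no post-vaccination endpoint can have 220 participants.* The Safety Set can reach 220, and solicited reactions, unsolicited AEs and SAEs are primary endpoints in both arms.
- *That a promised precision is not delivered.* Sections 11.1 and 11.2 describe precision only in words. No interval width is stated, and ±6.8, ±8.6 and ±11.4 points are all compatible with them.
- *That intervals will be computed on 300 records treated as independent.* This needs all 80 naïve participants to take a booster (220 + 80 = 300) and both records to be pooled. Nothing prescribes that. As an illustration only, the standard error would be understated by the factor √(1 + 2·80·ρ/300), which is 1.125 at a within-person correlation of 0.5 and 1.238 at 1. Uptake and correlation are both assumptions.

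Nor does section 11.4.2.1 prescribe a cross-arm antibody summary. It gives GMTs for each group, without defining group, and the antibody schedules are listed by arm. Naïve Day 57 and booster Day 29 are in fact aligned at 28 days after the last scheduled dose. The antibody part of the fix is a safeguard.

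**Conclusion.** The point holds for the safety summaries. The planned levels leave out the one level, the arm, at which the primary safety objectives are stated. The overall row estimates a mixture weighted 0.364 to 0.636 at full accrual. How far it misleads depends on the difference between arms, which the documents do not give: 6.4 and 3.6 points for an assumed 10-point difference, and nothing if the arms have the same rate.

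Three gaps go with it: the subgroup section covers four of eleven cohorts and does not tie hematologic versus solid tumor to an arm; boosted naïve participants are analysed in the booster group but left out of its totals; and the booster maximum is 140 in one place and 120 in another. These are matters of definition and reporting. They do not make the sample size or the planned interval methods wrong.

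**What to change.** **Section 11.4**
- Make the safety summary levels by arm (vaccine-naïve; booster) and by cohort, naming all eleven cohorts.
- Present hematologic versus solid tumor within arm.
- If a study-wide safety percentage is kept, count each person once and label it as a mixture of two regimens.
- Show boosted naïve participants as a distinct row in booster-group tables.
- State that antibody results are not pooled across arms at a shared day label.

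**Section 11.2**
- State the evaluable maxima as 80 for the naïve objectives and 140 newly enrolled for the booster objectives.
- Reconcile these with the 120 participants in six cohorts in section 3.1.

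**Cost.** Wording, a few table rows, and wider headline intervals: at a 50% rate, about 11.4 and 8.6 points against 6.8. No added participants, visits or samples.
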